4.4.4 Early Termination from the Study

Participants who are removed from the study after they receive IMP but do not complete the study may fall into one of these categories: Post-Treatment Early Termination or Dropout. If the participant has received IMP in at least one Experimental Session and completed one PCL-5 assessment beyond Baseline, they will be considered evaluable. All participants who receive IMP in at least one Experimental Session will be included in all safety analyses.

Participants can withdraw from treatment or withdraw consent at any time for any reason without judgment. The site team can withdraw a participant if, in their clinical judgment, it is in the best interest of the participant or if the participant cannot comply with elements of the protocol that are critical for safety or for the scientific integrity of the study. If the site team makes the decision to terminate the participant from treatment or the study, they will explain the reason for withdrawal and document in the participant's source records and Electronic Case Report Form (eCRF). If a participant develops any Exclusion Criteria that, in the opinion of the Medical Monitor or Investigators, affects the safety of the participant, including psychiatric diagnosis, medical diagnosis, pregnancy, or requirement of use of prohibited medications, the participant will discontinue treatment in Experimental Sessions but remain in the study for the associated Integrative Sessions. Any time a participant terminates from the study early, the site team will attempt to obtain information about AE outcomes if appropriate, as determined by the site physician and Medical Monitor. The site team will provide the participant with an Exit Plan/Plan for Moving Forward as described in Section 7.4.2 Exit Plan/Plan for Moving Forward.

Below are the definitions of the two types of participants who terminate the study after they receive IMP but before study completion:

- **Post-Treatment Early Termination**: Participants who discontinue study treatment but continues to participate in primary and secondary outcome assessments. Data collection will continue on the same schedule as planned through Study Termination visit procedures.

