9:55	Baseline BP, body temperature, pulse
10:00	IMP Administration
11:30	BP, body temperature, pulse
	Supplemental Dose Administration, unless tolerability issues emerge with the
	first dose, or it is refused by the participant.
17:30	C-SSRS, BP, body temperature, pulse

Pre-IMP administration

In the hours before IMP administration, the following procedures will take place:

- 24 to 48 hours prior to each Experimental Session, the site team will obtain the container assignment.
- On the day of the Experimental Session, the participant will arrive approximately 30 to 60 minutes prior to IMP administration.
- The site team will ensure the participant has not used caffeine or nicotine 2 hours prior and has fasted and not used cannabis or alcohol since 12:00 AM (midnight) prior to IMP administration and complied with all other requirements per Section 3.3 Lifestyle Modifications.
- The site team will inquire about any possible changes in health to ensure the participant continues to meet all eligibility requirements and record AEs as described in Section 10.0 Safety.
- The site team will instruct the participant that they will not be able to use caffeine or nicotine at least 6 hours after the IMP administration.
- The site team will complete urine drug screen, pregnancy test, and concomitant medication review.
 - A positive drug screen will be reviewed by the site physician and may be cause for delaying IMP administration to a later time, rescheduling the session to a later date, or withdrawing the participant from the study, based on Medical Monitor review.
 - A positive pregnancy test that has been confirmed is cause for withdrawal from the protocol.
- The therapy pair will administer Since Last Visit C-SSRS.
- The therapy pair will review procedures for the Experimental Session with the participant and discuss the participant's goals, intentions, and concerns and some of the commonly experienced effects of MDMA. The choice of whether to keep the dose the same or change it from the first Experimental Session will be made by the therapy pair in consultation with the site physician based on observed response, tolerability to the previously administered dose, and discussion with the participant.
- If the participant continues to be eligible, the session will proceed.

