10.1.7 Participant Discontinuation or Withdrawal from Study

Reasons why a participant may discontinue or be withdrawn from the study may include but are not limited to:

- Development of toxicity which in the investigator's judgment precludes further therapy
- Participants request
- Participant non-compliance
- Intercurrent illness
- At the discretion of the investigator
- Pregnancy
- Study termination by the sponsor
- Protocol violation

When a participant is withdrawn, the investigator will notify the sponsor and clearly document in the medical record and appropriate case report form the reason for withdrawal from study. When possible, the investigator will perform the procedures indicated for the final visits within 30 days after the last medication dose.

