10.3.3 Follow-up Requirements

Details of all pregnancies in study participants and their partners will be collected after Enrollment (Visit 0) and collected through 10 days after the last Experimental Session. Pregnancies should be reported to the sponsor via telephone or email within 24 hours of site staff awareness.

In the event of a pregnancy, the participant will discontinue Experimental Sessions but may continue with non-drug Integrative Sessions, PCL-5 assessments, and Study Termination procedures. At a minimum, prior to withdrawal from the study, efforts should be made to assess the final PCL-5 immediately and complete Study Termination procedures.

The investigator will collect follow-up information on the participant or their partner and neonate and forward to the sponsor until the outcome of the pregnancy, which will be reported on an optional Pregnancy eCRF. Any termination, elective or spontaneous, will be reported. Abnormal pregnancy outcomes, such as spontaneous abortion, fetal death, stillbirth, congenital abnormalities, or ectopic pregnancy, will be reported as SAEs.

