11.3 Prohibited Medications

There are medications that should be discontinued prior to enrolling in the study. These medications should not be restarted until study termination unless previously discussed with the MPBC medical monitor.

To be enrolled in the study, participants must:

- Refrain from the use of any psychoactive medication not approved by the research team from Baseline through Study Termination (with the exception of gabapentin or certain opioids for pain control).
- Agree to follow an appropriate tapering initiated at enrollment visit, defined by the treating physician, and to respect a subsequent washout period of 5 half-lives of the medication (calculation based on parent or active metabolite half-life, whichever is longer) preceding Visit 3.
 - o For specific medications, including antidepressants and most antipsychotics, refer to the Allowed and Prohibited Medication List (if a drug is not in the list, it will be discussed with the Medical Monitor).
 - For non-selective irreversible MAOIs, a 2-week washout period following the taper is required (three weeks in the case of imipramine and clomipramine, tricyclic antidepressants with MAOI activity) prior to Experimental Session.

Use of St. John's Wort, and other herbs and medicines with notable serotonergic effects are prohibited from Baseline to Study Termination.

Ketamine must be discontinued 1 month prior to Preparatory Session 3 (Visit 3) and is prohibited until Study Termination.

If an SSRI, SNRI, MAOI (including non-psychiatric medications with MAOI activity, e.g. rasagiline, selegiline, linezolid), or other antidepressant (including antipsychotics used for depression, e.g. clozapine, risperidone, aripiprazole, ziprasidone, olanzapine) is used between Experimental Session 1 (Visit 4) and Study Termination (Visit 16), the participant will be withdrawn from treatment and continue in follow-up.

Opioids other than hydrocodone, morphine, and codeine are prohibited from Enrollment Confirmation to Study Termination. Participants taking prohibited opioids will be cross-tapered to an allowable opioid during the Preparatory Period.

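### The protocol does not consistently separate stopping Experimental Sessions from leaving the study: its pregnancy rules conflict, and for other reasons it leaves Visit 16 data collection unsettled

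*Protocol*

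**What the plan says.** On pregnancy, five places in the protocol speak, and they do not agree.

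- Section 7.3.1, in the checks before dosing: "A positive pregnancy test that has been confirmed is cause for withdrawal from the protocol".
- Section 10.1.7 opens with "Reasons why a participant may discontinue or be withdrawn from the study may include but are not limited to" and includes pregnancy in the list.
- Section 4.4.4 covers a newly developed exclusion criterion that the Medical Monitor or investigators consider to affect safety. It names pregnancy and says "the participant will discontinue treatment in Experimental Sessions but remain in the study for the associated Integrative Sessions".
- Section 10.3.3: "the participant will discontinue Experimental Sessions but may continue with non-drug Integrative Sessions, PCL-5 assessments, and Study Termination procedures". It also asks for a final PCL-5 and the termination procedures before anyone is withdrawn.
- Section 10.1.6 allows non-drug participation in some cases only, after sponsor and IRB/IEC approval and renewed consent.

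On other reasons, 7.3.1 says that a positive drug screen "may be cause for delaying IMP administration to a later time, rescheduling the session to a later date, or withdrawing the participant" from the study, after Medical Monitor review. The 10.1.7 list also contains toxicity, intercurrent illness, non-compliance and protocol violation. Where feasible, "the investigator will perform the procedures indicated for the final visits within 30 days after the last medication dose". Section 11.3 says of antidepressants and MAOIs used during treatment that "the participant will be withdrawn from treatment and continue in follow-up".

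Section 4.4.4 defines a status, Post-Treatment Early Termination, for people who stop treatment but keep giving outcome data on the planned timetable up to the termination visit. Section 7.4 instead has participants who stop treatment complete the termination assessment at the moment of withdrawal. Section 8.4 sets the aim of complete data, including from those who discontinue treatment.

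**The concern.** Stopping the drug and leaving the study have different consequences for the data. After the first, the planned assessments can go on; after the second, they end. Where the text does not say which one a given event triggers, the site decides, and similar participants can end up with different data.

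At stake are the Visit 16 values of the primary measure (PCL-5) and the secondary measure (SDS), and the scheduled C-SSRS and AE collection that would have followed. The primary analysis is an MMRM. SAP 8.2 gives no rule for missing PCL-5 values and no sensitivity analysis. If people who leave after toxicity or a positive drug screen were doing worse than their earlier scores suggest, the model would not correct for it.

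**Working it through.** The plan has no figure to reproduce here. Its sample size has no statistical basis (Protocol 13.1), and it states no expected dropout for this study.

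**Step 1: compare the rules reason by reason.**

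- Pregnancy: 7.3.1 points to withdrawal from the protocol. Section 4.4.4 keeps the participant in the study. Sections 10.3.3 and 10.1.6 sit between, on different conditions. This is a contradiction.
- Positive drug screen: 7.3.1 offers delay, rescheduling or study withdrawal. It does not mention the option of stopping sessions while remaining for assessment, which 4.4.4 defines. This is a gap.
- Toxicity and intercurrent illness: 10.1.7 permits study withdrawal. Section 4.4.4 keeps in the study a participant with a new medical diagnosis that is an exclusion criterion. The two overlap only in part.
- Non-compliance: 10.1.7 permits study withdrawal, and 4.4.4 also lets the site withdraw someone "if the participant cannot comply with elements of the protocol that are critical for safety or for the scientific integrity of the study". The two agree.
- Prohibited antidepressants and MAOIs: 11.3 keeps the participant in follow-up. Sections 7.3.1 and 10.1.7 do not name this reason, so there is no direct conflict.

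**Step 2: can the final procedures in 10.1.7 stand in for Visit 16?** Table 1 of the protocol places Session 2 at 21 to 56 days after Session 1, Session 3 at 21 to 56 days after Session 2, and Visit 16 at 24 to 32 days after Session 3.

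- Visit 16 counted from the first dose: 21 + 21 + 24 = 66 days to 56 + 56 + 32 = 144 days.
- Visit 16 counted from the second dose: 21 + 24 = 45 days to 56 + 32 = 88 days.

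The 10.1.7 limit is day 30 after the last dose. For someone withdrawn after one session, that is at least 66 − 30 = 36 days short of the planned Visit 16; after two sessions, at least 45 − 30 = 15 days short. The pregnancy and drug tests at Visits 8 and 12 are done 21 to 56 days after the previous dose, so a result on days 31 to 56 arrives after the 30-day limit has passed.

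**Step 3: what would be missing.** By Table 6, the PCL-5 is taken at Visits 3, 6, 10, 14 and 16, and the SDS only at Visits 3 and 16. A participant who leaves at Visit 8 should normally have one post-baseline PCL-5 (Visit 6) for the MMRM. Unless final procedures are done, that participant has no post-baseline SDS.

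**Step 4: illustrative size, entirely on assumptions.** Shift in the observed-case mean change = f × D. Here f is the share without Visit 16 data, and D is how much worse their true mean PCL-5 change is than that of those observed.

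- f = 2%, D = 5: 0.02 × 5 = 0.1 points.
- f = 15%, D = 30: 0.15 × 30 = 4.5 points.
- f = 7.5%, the Phase 2 dropout quoted in Protocol 1.2.4 (8/107 = 7.48%): 0.075 × 5 = 0.375 to 0.075 × 30 = 2.25 points.

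For scale, with an assumed SD of 20 and N = 100 the standard error is 20/√100 = 2.0 points; SDs of 15 and 25 give 1.5 and 2.5.

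**The case against.** A reader might infer that 7.3.1 and 10.1.7 end participation for drug use, toxicity and non-compliance while 4.4.4, 10.3.3 and 11.3 stop only the drug, so that data are lost selectively in participants who do badly. The documents do not support that. The drug-screen rule has two other outcomes, and the 10.1.7 list is permissive. Section 4.4.4 itself allows site withdrawal. Section 10.3.3 deals with pregnancy only, and 11.3 with named drug classes. Pregnancy, the one clear contradiction, is not a marker of poor response.

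The protocol also has safeguards. Section 10.3.3 asks for a final PCL-5 before withdrawal. Section 4.4.4 asks sites to seek AE outcomes and retains data already collected. Sections 10.1.2, 10.1.3 and 10.1.5 follow reported SAEs and AESIs to outcome. The 7.3.1 checks come before dosing. At Session 1 nobody has yet been dosed, and the participant would be a Pre-Treatment Early Termination. At Sessions 2 and 3 at least 21 days have passed, so the 14 days of calls and the PCL-5 due at days 10 to 18 should already be complete. The MMRM also uses earlier PCL-5 scores and would remove the part of any bias that those scores explain.

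All of this stands, and it limits the point. It does not resolve the conflict on pregnancy or on the timing of the final assessment. The safeguards preserve an early value and follow known events; they do not supply a Visit 16 value or detect new events after the participant has left.

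**Conclusion.** The protocol contradicts itself on whether a participant who becomes pregnant stays in the study, and on when someone who stops treatment has the final assessment. For a positive drug screen, toxicity, intercurrent illness and protocol violation the fault is smaller: study withdrawal is allowed, and the alternative that keeps data collection going is not mentioned. For general non-compliance, 4.4.4 and 10.1.7 are consistent.

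Visit 16 and later safety data may therefore be lost or collected off schedule, contrary to the aim in 8.4. Loss tied to outcome is possible in the toxicity and drug-screen cases but is not shown. The documents give no basis for its size. The range of 0.1 to 4.5 points rests on assumed f and D, assumes that nobody lost has a usable final PCL-5, and ignores what the MMRM recovers. The 7.5% figure is all-cause dropout from earlier studies, not a rate for these reasons. The wording should be corrected because the correction is cheap, not because a large bias has been demonstrated.

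**What to change.** Reconcile 7.3.1, 7.4, 10.1.6, 10.1.7 and 10.3.3 with 4.4.4 on data collection only.

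- State that a participant who stops Experimental Sessions for any of these reasons is by default asked to continue PCL-5, SDS, C-SSRS and AE collection on the planned schedule through Visit 16. The exceptions are withdrawal of consent and a documented site decision that study withdrawal is necessary. In pregnancy, continuation remains subject to the 10.1.6 approvals.
- State whether the assessment in 7.4 is additional to Visit 16 or replaces it. Visit 16 is dated from Experimental Session 3, so say also how it is dated for someone who has no third session.
- Record treatment discontinuation and study withdrawal in separate eCRF fields, each with its reason.

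Every decision about stopping MDMA, and which of the conflicting clinical rules applies, stays with the sponsor. The cost is minor protocol wording, one added eCRF field and a few follow-up visits that 4.4.4 already plans.
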